9. RESEARCH DESIGN AND METHODS

Overview: This pilot trial is a Phase IV, 12-week, single center, randomized, double blind, parallel group comparison of low (0.5 mg twice daily with slower titration over one full week) versus standard dose (1.0 mg twice daily with standard titration) varenicline in SMI individuals with DSM-V BD or SSD with a 12-week, post-treatment follow-up (see Figure 3 for study design). The 16 visits after screening (Weeks 0-24) will take place using the guidelines developed by the UCSD Office of the Vice Chancellor for Research. Participants will be screened, randomized and follow the protocol according to the Research Ramp-Up phase under which the university is operating at that time of (i.e., orange, yellow, or green).

Full participation includes 14 treatment visits and 3 follow up visits. All in-person visits will take place at Pac-TARC. In addition to testing low dose varenicline in SMI smokers for the first time, three other innovative design features are incorporated to try to improve medication tolerability and short-term quit rates. 1) Plasma will be obtained at baseline to measure participants' NMR and to identify slow versus normal nicotine metabolisers. 2) A flexible quit date (between days 8-35) will be employed allowing varenicline preloading to occur prior to the TQD. 3) Ten sessions of ACT for smoking cessation will be delivered by trained counselors first in 7 in-person sessions followed by 3 sessions delivered via telephone to all participants. Randomization of participants will occur in a 1 (low dose) to 1 (standard dose) ratio and participants will be balanced on diagnosis (BD vs SSD), gender, race (White vs. non-White) and whether or not they are taking antiepileptic medications (e.g., carbamazepine) as mood stabilizers (20) which, like the demographic/ethnic factors (11,26) can influence CYP2A6 activity and affect the NMR. Volunteered, observed and solicited NPSAEs will be assessed using standardized procedures developed in EAGLES and our other prior work (4,27). However, going beyond EAGLES, we will also assess participants' tobacco withdrawal symptoms, urges to smoke, sleep disturbances, self-efficacy & confidence to quit, and satisfaction with the protocol elements. To further extend EAGLES, we will include more "real world" participants who are somewhat less psychiatrically stable and who have comorbid substance use disorders (SUDs) in early remission.

Figure 3. Study Design – ACTSLOW Pilot Trial

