With the exception of red phase, participants who have been telephone screened and determined eligible for the screening process will be invited to participate in the study. Following UCSD's Research Ramp-Up phases of operation, participants will be screened and treated in accordance to the following protocols described

below. All telephone or tele-video visits will be completed on a HIPAA compliant app called Doximity (<https://www.doximity.com/about/research>)

Table 3. Schedule of Assessments

Assessments	Study Weeks															
	-2	0	1	2	3	4	5	6	7	8	9	10	11	12	16	20
Diagnostic Assessments																
MINI ¹	X															
Nicotine Metabolite Ratio		X														
Medical History	X															
TLFB ² for Drinking & Drug Use	X	X	X	X	X	X	X	X	X	X	X	X	X	X	X	X
Smoking-Related & Abstinence Verification Measures																
FTCD ³	X															
Smoking Diary/NUI ⁴	X	X	X	X	X	X	X	X	X	X	X	X	X	X	X	X
QSU ⁵ -Brief		X	X	X	X	X	X	X	X	X	X	X	X	X	X	X
MNWS ⁶	X	X	X	X	X	X	X	X	X	X	X	X	X	X	X	X
SEQ-12 ⁷ & Confidence Scale ⁸	X								X			X			X	
Urine Cotinine	X											X			X	
Expired CO Smokerlyzer	X	X	X	X	X	X	X	X	X	X	X	X	X	X	X	X
Mood, Sleep, & Suicidality-Related Measures																
HADS ⁹	X	X	X	X	X	X	X	X	X	X	X	X	X	X	X	X
Insomnia Severity Index	X	X	X	X	X	X	X	X	X	X	X	X	X	X	X	X
ASRM ¹⁰	X	X	X	X	X	X	X	X	X	X	X	X	X	X	X	X
C-SSRS ¹¹	X	X	X	X	X	X	X	X	X	X	X	X	X	X	X	X
Safety & Tolerability																
General Adverse Events	X	X	X	X	X	X	X	X	X	X	X	X	X	X	X	X
NAEI ¹²	X	X	X	X	X	X	X	X	X	X	X	X	X	X	X	X
Concomitant Medications	X	X	X	X	X	X	X	X	X	X	X	X	X	X	X	X
Urine Pregnancy Test	X	X														
Urine Drug Screen	X															
Satisfaction & Protocol/Study Medication Adherence																
ACT Treatment Satisfaction Questionnaire				X			X		X							
CSQ-8 ¹³			X	X	X	X	X	X	X	X	X	X	X	X	X	X
Pill Counts		X	X	X	X	X	X	X	X	X	X	X	X	X	X	X
ACT Mechanism of Change																
Avoidance & Inflexibility Scale	X					X			X	X	X	X	X	X	X	X

¹Mini International Neuropsychiatric Interview (MINI), Version 7.0.2 for DSM-V; ²TimeLine Follow Back (TLFB); ³Fagerstrom Test for Cigarette Dependence (FTCD); ⁴Nicotine Use Inventory (NUI);

⁵Questionnaire of Smoking Urges-Brief (QSU-Brief); ⁶Minnesota Nicotine Withdrawal Scale (MNWS);

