operation, at baseline and throughout the study: **Minnesota Nicotine Withdrawal Scale** (MNWS; 31) to monitor symptoms of tobacco withdrawal; **Questionnaire of Smoking Urges-Brief** (QSU-Brief; 32) to measure cravings to smoke; the **TLFB for Alcohol and Drug Use** (33,24); the **Nicotine Use Inventory** (NUI; 4, 27) is a brief questionnaire that has been used throughout the varenicline Phase III-IV trials that monitors smoking rates and probes for other forms of nicotine use including e-cigarettes, hookah, cigars, etc; the **Hospital Anxiety and Depression Scale** (HADS; 35) is comprised of two separate 7-item self-report questions assessing anxiety and depressive symptoms, respectively; the **Altman Self-Rating Mania Scale** (ASRM; 36) is a 5-item self-rating mania scale with a scoring range from 0-20 that assesses symptoms of mania and hypomania; the **Columbia-Suicide Severity Rating Scale** (C-SSRS; 37) is a semi-structured interview conducted by trained raters to monitor suicide ideation and behaviors; the **Insomnia Severity Index** (ISI; 38) is a reliable and valid 7-item self-report measure to evaluate perceived sleep difficulties; the **Avoidance and Inflexibility Scale** (AIS; 41) is a 27-item questionnaire measuring changes in acceptance-based processes of smoking cessation based on this technique's hypothesized mechanism of action; the **Neuropsychiatric Adverse Events Interview** (NAEI) is a 25-item questionnaire that was used in EAGLES (4) and our prior work (27) to probe for neuropsychiatric complaints that might qualify as adverse events in a clinical trial; an **Assessment of General AEs** using standard operating procedures to record AEs according to the Medical Dictionary for Regulatory Activities version 18.0 (MedDRA; 44) – derived preferred terms; and the **Self Efficacy Questionnaire** (SEQ-12; 42) and **Confidence to Quit Scale** (43) measuring participants' self-efficacy and confidence to quit smoking. Study medication will be dispensed to participants by mail per VMRF pharmacy's shipping protocol with instructions on its use. Participants will also have their first session of ACT session (see below) at their week 0 baseline visit. All assessments will be performed by telephone (on HIPAA compliant Doximity) as scheduled with the exception of vitals, urine or blood collection, and exhaled CO which will not be collected during this Red phase.

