Non-Treatment Follow-up Visits (weeks 13-24): Following discontinuation of the medication participants will be followed every 4 weeks until conclusion of the study assessing mood, any suicidal thinking, and nicotine or other drug use. Visits for study weeks 16 and 20 will be done via telephone and take approximately 30-45 minutes. The final visit at week 24 will take place at Pac-TAC and take approximately 1 hour to complete.

Medication Adherence: Although aware of their limitations, due to budgetary constraints we will use participant self-report and pill counts of capsules returned at the biweekly visits as the measure of study medication adherence. Compliance will be defined as having any (partial or full) daily dose of study drug for 80% of the planned treatment period of 84 days.

Medication Tolerability Outcome Measure - - We will also assess: 1) % participants in each dosing arm who tolerate twice daily dosing with no dosage reductions; 2) % participants in each arm who continue on treatment but with a dosage reduction to once daily dosing; 3) % participants who discontinue medication treatment, but continue in study (off treatment/in study; treatment discontinuation rate); and 4) % participants who discontinue treatment and study enrollment (e.g., study discontinuation rate).

Assessment of NPSAEs & 2° NPS safety outcome: We will use the identical procedures we helped develop and used in the EAGLES trial to monitor neuropsychiatric safety (7). Briefly, all NPS complaints that are volunteered, observed or solicited with the NAEI; any elevated scores on the mood-, sleep- and suicidality-related measures described above, and any proxy reports from collateral informants will be evaluated as potential NPSAEs by the study team. Each AE will be rated by one of the study clinicians as to its intensity using the standardized EAGLES procedure: Mild = no or minimal interference in functioning; Moderate = some interference in functioning; Severe = significant interference with functioning. Based on this scoring, we will determine the composite safety endpoint used in EAGLES (i.e., NPSAEs that were rated as moderate to severe across the 16 pre-specified domains). We will also examine the observed incidence of participants experiencing NPSAEs of any intensity (i.e., mild, moderate or severe) as our 2° NPS safety outcome during the 12-week active treatment phase plus 28 day as also done in EAGLES.

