2° Efficacy Outcome: In keeping with the pilot nature of this trial, we will use 7-day point prevalence abstinence (PPA) at week 12 confirmed by expired CO levels ≥ 4 ppm and urine cotinine levels < 200 mg/ml as the secondary efficacy endpoint. We will continue to track smoking outcomes through week 24 using these same biochemical verification measures to assess 7-day PPA at week 24 as a tertiary outcome.

Other Secondary Outcome Measures: Our gathering of data on the MNWS, QSU-Brief, ISI, SEQ-12, Confidence to Quit Scale is exploratory in nature and is intended to provide preliminary information on the mechanism of action of combined varenicline and ACT in SMI smokers and their relation to NPSAEs. We will also explore ACT's effects on avoidance and inflexibility with the AIS at weeks 12 and 24.

Determination of the NMR: The ratio of trans-3'-hydroxycotinine (3HC) and cotinine (COT) will be measured in plasma using electrospray ionization liquid chromatography tandem mass spectrometry (ESI LC-MS/MS) technology adapted from the protocols described by Tanner et al. (45) and Lerman et al. (7). COT and 3HC in plasma will be determined by quantifying with standard deuterium labeled COT and 3HC, known as COT-d3 and 3HC-d3 (commercially available from Sigma-Aldrich). Plasma samples will be spiked with a known amount of COT-d3 and 3HC-d3, and samples will be subjected to MS to quantitate the endogenous levels of COT and 3HC by parallel reaction monitoring. LC-MS/MS will be performed on the high-resolution Orbitrap Q-Exactive LC -MS system located in the [name] lab in the Skaggs School of Pharmacy and Pharmaceutical Sciences. Standard plots of different amounts of deuterated and non-deuterated COT and 3HC standards into control plasma, followed by LC-MS/MS, will define the linear range of quantitative measurements, lower limit of detection, and reproducibility of replicate samples. Ratios of 3HC/COT will be calculated from quantitative MS data analyzed by the Skyline software. Reliability of these procedures in plasma is high with NMR measurements robust even to differences in analytic methods used by different laboratories (45). The NMR data will be compiled with the phenotypic data of this study to examine the relationship of NMR to NPSAEs and smoking cessation.

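### A raised Insomnia Severity Index score is one route into NPSAE review, so part of any positive ISI–NPSAE association in the exploratory analysis is built in

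*Combined protocol and SAP*

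**What the plan says.** All references are to section 9 of the combined protocol and SAP unless stated.

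- *Assessment of NPSAEs & 2° NPS safety outcome* lists the sources of candidate events: complaints that are volunteered, observed or elicited by the NAEI interview, proxy reports, and "any elevated scores on the mood-, sleep- and suicidality-related measures described above". All of these "will be evaluated as potential NPSAEs by the study team". The secondary safety outcome is the proportion of participants with an NPSAE of any intensity during the 12 treatment weeks plus 28 days.
- Table 3 places the ISI under "Mood, Sleep, & Suicidality-Related Measures", with the HADS, ASRM and C-SSRS. The baseline visit text says that the ISI "is a reliable and valid 7-item self-report measure to evaluate perceived sleep difficulties".
- *Other Secondary Outcome Measures* states: "Our gathering of data on the MNWS, QSU-Brief, ISI, SEQ-12, Confidence to Quit Scale is exploratory in nature". The purpose given is preliminary "information on the mechanism of action of combined varenicline and ACT in SMI smokers and their relation to NPSAEs".
- On the source trial, the same NPSAE paragraph says "We will use the identical procedures we helped develop and used in the EAGLES trial to monitor neuropsychiatric safety". The *Overview* begins a list that includes sleep disturbances with "However, going beyond EAGLES, we will also assess".
- Table 1 in section 7 has a sleep disorders row within NPSAEs of any severity.

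**The concern.** The ISI has two roles. It is the explanatory measure in the exploratory analysis, and a high value on it is one of the ways in which the outcome is found. The outcome also contains the content of the scale, since insomnia-type events are themselves NPSAEs of any intensity. A high ISI score can therefore go with a recorded NPSAE even if sleep had no link at all with mood, psychotic or suicidality events.

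What is at stake is how a mechanism finding is read. A reported link between poor sleep and neuropsychiatric events could partly restate that insomnia was detected with an insomnia scale. If the route of detection is not captured at the time, it may not be possible to separate the two later.

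**Working it through.** The plan gives no figure for the ISI–NPSAE association, so there is nothing to reproduce. The check is mainly a comparison of passages, followed by an illustration.

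**1. Does the trigger rule cover the ISI?** The rule speaks of sleep-related measures already described. The ISI is the only sleep scale in the protocol, and Table 3 groups it with the mood and suicidality scales. The rule must therefore include it. The other four scales named in the exploratory sentence (MNWS, QSU-Brief, SEQ-12, Confidence to Quit Scale) sit under the smoking-related heading of Table 3, so among those five the problem is specific to the ISI.

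**2. Is the ISI then set against NPSAEs?** The wording is loose: *their* could refer to the scales or to the mechanisms that they index. On either reading, ISI data are what would be related to NPSAEs.

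**3. Does the outcome contain sleep events?** In Table 1, among varenicline-treated bipolar participants, 45.3% had any psychiatric AE and 26.7% had a sleep event. Hence 26.7 / 45.3 = 0.59, so about 59% of those with any event had a sleep event. Some overlap of content would exist even without the trigger.

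**4. Does anything separate the two roles?** The documents do not provide for recording the detection route, excluding sleep or ISI-found events, requiring the ISI to precede onset, or blinding raters to the score. They give no cutoff for an elevated ISI.

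**5. Illustration of the detection component alone.** Let b be the probability of an NPSAE recorded by other routes, assumed independent of the ISI. Let q be the assumed probability that a raised ISI adds an NPSAE that would otherwise go unrecorded. Then

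- P(NPSAE | raised ISI) = b + (1 − b)q
- P(NPSAE | not raised) = b
- OR = {[b + (1 − b)q] / [(1 − b)(1 − q)]} / {b / (1 − b)}

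For b, the Table 1 varenicline (0.453) and placebo (0.281) rates serve as a range. Values of q are assumptions; no document supplies them.

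| q | b = 0.453: P if raised | OR | b = 0.281: P if raised | OR |
|---|---|---|---|---|
| 0.10 | 0.5077 | 1.25 | 0.3529 | 1.40 |
| 0.25 | 0.5898 | 1.74 | 0.4608 | 2.19 |
| 0.50 | 0.7265 | 3.21 | 0.6405 | 4.56 |

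Example: b = 0.453, q = 0.10 gives 0.453 + 0.547 × 0.10 = 0.5077; odds 0.5077 / 0.4923 = 1.031; reference odds 0.453 / 0.547 = 0.828; OR = 1.25.

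The OR exceeds 1 whenever q > 0. If events found only through the ISI are left out of the outcome, q = 0 and the OR in this illustration returns to 1.0. The overlap of content in step 3 comes on top and is not in these figures.

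**The case against.** **A raised score is not an event.** It prompts evaluation, and the same complaint may also surface through the NAEI or spontaneous report. This stands: the extra yield of the ISI could be small. It limits the size of the bias but does not remove it.

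**The analysis is exploratory and barely specified.** No formal testing is planned and no model, timing or outcome version is given. A baseline ISI could be used, and a pre-treatment score cannot trigger a treatment-emergent event. This also stands, and it is part of the remedy. But nothing in the plan requires that choice, and a baseline score alone does not deal with sleep events being part of the outcome.

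**Sleep events matter in their own right.** Section 7 stresses insomnia, abnormal dreams and sleep disorders, so dropping them would lose information. This is a good reason to keep the all-NPSAE result and add to it.

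**The ISI schedule is the same in both arms.** That stands. The point is not about the dose comparison.

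Some stronger readings are tempting but not supported:

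- *That NPSAE incidence is raised by an undisclosed route.* The NPSAE paragraph names the scale-score route openly.
- *That this route shows a departure from EAGLES.* The two statements about EAGLES sit uneasily together, but the documents do not show whether EAGLES used a sleep-scale trigger, and the *Overview* list concerns what is assessed, not how events are adjudicated. The analytic plan uses EAGLES rates as a comparator only for abstinence.
- *That the bias can be sized from Table 1 and compared with the effects of d = 0.30 to 0.40 in Sample Size Determination.* Assigning shares of Table 1 sleep events to high ISI scores would mix overlap of content with the detection artefact, in bipolar participants only. The quoted d values illustrate confidence-interval precision for 30 per arm; they are not a benchmark for this association.
- *That the result is meant to guide the later RCT.* No passage says so for the ISI–NPSAE relation.

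**Conclusion.** The point holds in limited form. Following the plan as written, part of any positive association between the ISI and NPSAEs of any intensity is built in, through the detection rule and through the inclusion of sleep events in the outcome. The direction is upward. The size cannot be determined from the documents; the odds ratios of 1.25 to 4.56 are illustrative, resting on assumed values of q from 0.10 to 0.50 and on Table 1 rates. Those rates come from bipolar participants, whereas this trial plans 30 with bipolar disorder and 30 with schizophrenia spectrum disorder, half of all participants on the low dose.

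The consequence is confined to this exploratory secondary analysis. Aim 1 is unaffected. A reader might extend the point to the moderate-to-severe composite, but its 16 domains are not listed, so the documents do not show whether sleep events enter it.

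**What to change.** 1. Add a field to the adverse event form recording every route by which each NPSAE was found, using the categories the plan already names: volunteered, observed, NAEI, scale score (stating which scale) and proxy.
2. In the exploratory analysis, keep the relation of the ISI to all NPSAEs as descriptive. Beside it, report the relation of the ISI to NPSAEs that are not sleep events and were not found solely through an ISI score, using the Week 0 ISI or the ISI from the visit before onset. Base any mechanism statement on this second result. Week 0 is the simpler choice because it is defined for participants without an event too.
3. Report NPSAE incidence with and without events found only by a scale score. Reconcile the claim of identical procedures with the *Overview* statement that assessing sleep disturbances goes beyond EAGLES.

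The cost is one form field, a few lines in the analytic plan and fewer events in the restricted analysis. As a rough guide, if the Table 1 varenicline rates applied to all 60 participants, at least 45.3% − 26.7% = 18.6%, or about 11 people, would have a non-sleep event. If sleep and non-sleep events were independent, the figure would be 0.186 / 0.733 = 25.4%, or about 15. Removing events found only through the ISI could lower this further. No visit, procedure or treatment changes.

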For each feasibility measure we will compare study values to the targeted benchmarks which are based on our prior work in SMI smokers (4,49) and the relevant literature (13,19). While formal hypothesis testing is not planned given the pilot nature of this proposal (50,51), we will calculate effect sizes (i.e., Cohen's d or odds ratios [ORs]) and standard deviations, as well as confidence intervals (CI), for our feasibility variables and use

them as preliminary data for the subsequent larger RCTs. We will also calculate and examine Cohen's kappa coefficients for our clinician-obtained measures including the MINI, TLFB, C-SSRS, and assessments of NPSAEs and general AEs. These values will be used to assess the inter-rater reliability of relevant measures in SMI smokers and to refine our rater training procedures if necessary.

Aim 2: Explore whether nicotine clearance rate as measured by the NMR influences the incidence of NPSAEs in varenicline-treated SMI smokers. This exploratory aim will begin to test the **hypothesis** that incidence of NPSAEs of any severity will be higher in slow nicotine metabolisers assigned to standard dose varenicline compared with normal metabolisers treated with low dose varenicline.

To gather preliminary data on the NMR, the frequency distributions of the NMR values in this SMI sample will be compared with the published data from Lerman et al. (2015) in a large sample of NMI smokers that found a cutoff score of 0.31 as the demarcating point between slow (<0.31) and normal (including rapid) metabolisers. Based on this analysis, we will calculate Cohen's d effect sizes comparing slow metabolisers on standard dose vs. normal metabolisers on low dose, as well as standard deviations and CIs, for incidence of NPSAEs of any severity to examine the direction and magnitude of the effect. Secondary outcome measures will also be examined using the same methodologies including 7-day PPA at weeks 12 and 24, to guide future studies. Regarding the secondary efficacy outcomes, and anticipating possible quit-boosting effects from ACT and varenicline preloading, we predict 7-day PPA rates at week 12 will be at least comparable to those observed in varenicline-treated EAGLES SMI participants which was 28.2%, and that 7-day PPA rates at week 24 will be at least comparable to the 20.0% observed in EAGLES (unpublished data). To examine the possible confounding effect of variable lengths of abstinence depending on when participants first attempt to quit smoking within the quit window, we will examine the effect of a time factor (i.e., the number of days from the first dose of medication to the date of the first quit attempt) with the methodologies described above.

Sample Size Determination: The aims of this pilot trial are to gather preliminary data or demonstrate proof of principle with potential for high impact within one or more stated research priorities of the funding agency. Thus, Aim 1 of the proposal addresses feasibility while Aim 2 is exploratory and begins to test the principle as to whether NMR influences NPSAE propensity and medication tolerability in SMI smokers by estimating effect sizes. The study is designed to provide preliminary data on the feasibility of a larger RCT that would further develop these novel pharmacotherapy approaches in SMI smokers. It is not powered to test clinical outcomes, thus, safety (incidence of NPSAEs) and efficacy (7-day PPA at week 12 and at week 24) outcome measures are considered secondary endpoints. In our group's previous work with varenicline in EAGLES (4) and another trial done in SMI smokers (49), we randomized ~80% of those screened and retained >80% of study participants. Similar retention rates were found in another pilot trial of varenicline in bipolar smokers (52) and in [name] preliminary study. Therefore, we expect that with N=60 we will be able to adequately determine the feasibility of the proposed study procedures.

Consistent with recommendations on the proper sizing for pilot studies literature (50,51,53), we chose a sample size of 60 participants based on maximal accrual expectations over a 15-month recruitment period and practical cost constraints to conduct a pilot trial in this special population of smokers. Previous studies examining target sample sizes for pilot studies have argued that as few as 12 participants per group is adequate to estimate standard deviations for a two-group study (54,55), while others have suggested that a total sample of 30 is an acceptable size for a pilot study (56). With a sample of 60 (n=30 per dosing group), we will have the ability to estimate effect sizes, standard deviations, and their CIs with adequate precision to evaluate the feasibility of study procedures and to subsequently conduct formal power analyses for future RCTs (57). As such, it is amply sized as a pilot trial. For example, given a small-to-medium estimated effect of $d=0.40$, we would have 80% confidence that the true effect fell between 0.064 and 0.733 with a pilot sample of N=60. For a smaller effect of $d=0.30$, this 80% CI becomes 0.005-0.672 providing adequate precision in detecting an effect (i.e., zero not in the CI) for use in power analyses for a larger RCT. Furthermore, applying Sims' and Lewis' (2012) calculations, the sample size of N=60 will allow us to estimate standard deviations around our feasibility estimates with a minimal inflation factor (e.g., 1.09 for one-sided 80% CIs) for use in future RCT power analyses.

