Screening Visit (Week -2). Prior to the screening visit, participants will be mailed or emailed a blank copy of the informed consent form. Potential participants will be consented by phone/video conferencing using Doximity to orient them to the study procedures and requirements. Participant's decisional capacity will be assessed during consent by a trained research staff member to ensure they fully understand the study. After obtaining informed consent, participants will undergo a semi-structured clinical interview, the Mini-International Neuropsychiatric Inventory Version 7.0.2 for DSM-V (MINI; 28) administered by a trained research assistant. A standardized health assessment and mental status examination, including motivation to quit (29), will be

performed by a medical staff by using Doximity. The only in-person procedures conducted during this phase will be for medical procedures. Specifically, a urine sample will be obtained for on-site urine toxicology, baseline cotinine level, and pregnancy screening. Expired breath CO will be measured and blood pressure and heart rate will be obtained along with height and body weight. Lastly, the **Fagerström Test for Cigarette Dependence** (FTCD; 30), a standardized self-report questionnaire will be used to measure nicotine dependence severity and the **TimeLine Follow-Back (TLFB) for Alcohol and Drug Use** (33,24) which obtains estimates of daily drinking and drug use using a calendar technique will be used. The screening visit will take approximately 2-3 hours to complete in both its virtual and face-to-face forms and the latter will follow all guidelines to mitigate COVID-19 risk to participants and staff (see below).

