Treatment Follow-up Visits (Weeks 1-12). Table 3 illustrates the schedule of assessments for treatment follow-up visits. On Day 8 (week 1) participants will pick a day between 8 and 35 to be their target quit date considering that one goal of the study is to have participants take varenicline for several weeks before trying to quit to maximize effectiveness. In-person visits for study weeks 1, 3, and 5 will take approximately 30 minutes to complete as participants will have 30-minute ACT sessions, as described below. In-person visits for study weeks 2, 4, and 6 will take approximately 1 hour as participants will have ACT sessions, assessment of blood pressure and heart rate, and questionnaires to complete (see table 3). In-person visits for study weeks 8, 10, and 12 will take 30 minutes to complete as participants will not have ACT on these visits but will fill out questionnaires and have blood pressure/heart rate assessed. Telephone visits for study weeks 7, 9, and 11 will take ~35 minutes, as the last ACT sessions will be completed at these visits. Figure 3 illustrates the study design. In addition to the questionnaires given at baseline described above the following questionnaires will be given during the treatment phase: the **Client Satisfaction Questionnaire – 8** (CSQ-8; 39) is a standardized measure of treatment satisfaction that has been used widely across mental health services (40) and in smoking cessation research with varenicline preloading (18) and the **ACT Treatment Satisfaction Questionnaire (ACT-TSQ)** measures treatment satisfaction with ACT counseling using two force-choice response items and a Likert scale (9).

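### Does planning Cohen's kappa for the Timeline Follow-Back, with no variable or weights named, leave the reliability check unsound?

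*Combined protocol and SAP*

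**What the plan says.** The Aim 1 part of the Data Analytic Plan (section 9) gives one sentence to reliability statistics. It announces "kappa coefficients for our clinician-obtained measures including the MINI, TLFB, C-SSRS, and assessments of NPSAEs and general AEs". The next sentence gives the purpose: "These values will be used to assess the inter-rater reliability of relevant measures in SMI smokers and to refine our rater training procedures if necessary".

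The TLFB is described under the Screening Visit for the Orange Phase, and again for the Yellow and Green Phases, as a tool "which obtains estimates of daily drinking and drug use using a calendar technique". Neither place says how it is scored for a comparison between raters: days of use, amounts, or any use yes/no. No section names kappa weights or an intraclass correlation (ICC).

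The same part of the plan says that formal hypothesis testing is not planned because this is a pilot.

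**The concern.** One statistic is assigned to five kinds of measure. Ordinary kappa suits a yes/no or nominal call, such as a MINI diagnosis or the presence of an adverse event. The TLFB is the odd one out, because its raw output is quantitative.

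Unweighted kappa counts every disagreement as total. Raters who differ by a day here and there would get the same coefficient as raters who differ by many days equally often. The stated use is to judge whether raters need more training, and a coefficient that ignores the size of disagreement is a poor guide to that. At stake would be needless retraining, a missed need for it, or a misleading reliability figure carried into the larger trial that this pilot is meant to inform.

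**Working it through.** The plan states no kappa value, target, number of raters or number of double-rated participants, so there is no figure to reproduce. The check has three parts.

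**1. How unweighted kappa behaves on counts (assumed data)**

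Assumed inputs: 60 participants (the planned sample size), two raters, counts from 0 to 11 with five participants at each value, discordance in 60% of pairs, and equal rater margins. Every disagreement is 1 unit in case A and 6 units in case B.

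- Unweighted kappa = (observed agreement − chance agreement) / (1 − chance agreement). Observed agreement is 0.40 and chance agreement is 1/12 = 0.0833, so kappa = 0.3167 / 0.9167 = 0.345 in both cases.
- Quadratic-weighted kappa = 1 − (mean squared difference observed) / (mean squared difference expected by chance). The chance value is twice the variance of the counts: 2 × 143/12 = 23.83.
  - Case A: 1 − (0.6 × 1)/23.83 = 0.975.
  - Case B: 1 − (0.6 × 36)/23.83 = 0.094.
- The two-way absolute-agreement ICC is 0.975 and 0.095.

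So the statistical statement is correct. It is also true by definition. Unweighted kappa depends on how often raters differ, not on how far apart they are. Holding the discordance rate fixed and changing only the error size must leave it unchanged.

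**2. Less regular data (also assumed)**

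Simulated sets of 60 used count windows of 0–7, 0–14 and 0–28 days and three patterns of zeros: counts uniform over the window, 50% zeros, or 80% zeros. The second rater differed for 30% or 50% of users, by one day or by at least three days. Selected results, as means over the simulated sets:

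| Setting | Error size | Unweighted kappa | ICC | Any-use kappa |
|---|---|---|---|---|
| 0–7 days, 50% zeros, 50% discordant | one day | 0.64 | 0.98 | 0.96 |
| same | three days or more | 0.64 | 0.63 | 0.89 |
| 0–28 days, 50% zeros, 50% discordant | one day | 0.66 | 1.00 | 0.99 |
| same | three days or more | 0.66 | 0.76 | 0.98 |
| 0–7 days, uniform counts, 50% discordant | three days or more | 0.49 | 0.32 | 0.67 |

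For one-day errors, unweighted kappa is too low. For large errors it is close to or below the ICC where half or more of the counts are zero. It is too high only in the uniform settings, where 3% to 12% of counts are zero. Few zeros are unlikely for drugs other than cannabis, since section 10 excludes a positive screen for them. For alcohol and cannabis the documents do not settle it.

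**3. What depends on these values**

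- Feasibility benchmarks (Hypotheses 1a to 1c): accrual, recruitment cost, retention, completion of procedures and ACT sessions, quit attempts, medication adherence and satisfaction. None uses a kappa or a TLFB result.
- Safety: the secondary outcome is the "observed incidence of participants experiencing NPSAEs of any intensity", and the composite counts "NPSAEs that were rated as moderate to severe across the 16 pre-specified domains". Neither uses the TLFB.
- Aim 2: effect sizes are planned "for incidence of NPSAEs of any severity to examine the direction and magnitude of the effect". The TLFB is not involved.
- Efficacy: seven-day point prevalence abstinence at weeks 12 and 24 rests on smoking status with biochemical checks. The TLFB here covers alcohol and drugs.

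**The case for a change.** The strongest case for a change is that the plan names the TLFB explicitly, describes it as a daily estimate, and attaches kappa to it without qualification. Read literally, Cohen's kappa with no mention of weights is the unweighted form. Leaving the variable open also lets the choice be made after the data are seen. The remedy would be a line of text, and reliability figures from a pilot can shape the next trial.

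Part of this stands. The variable and weights are indeed missing, and unweighted kappa on counts would be a poor choice. What does not follow is that the plan commits to that choice. The sentence covers five instruments at once, and kappa suits most of them. It cannot be run on the TLFB until someone decides what the categories are, and that is the point at which any-use coding or weights would be chosen. A late choice also has little room to do harm, since no trial conclusion is drawn from the coefficient. For a rater check in a pilot, such scoring detail can reasonably sit in a rater manual.

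A separate question is whether paired ratings will exist at all, since the safety section has each adverse event graded by a single clinician. That bears on any agreement statistic and is not an argument about weights.

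**Conclusion.** The concern describes a real property of unweighted kappa, but not an error in this plan. The plan leaves a scoring detail open, and an analyst can be expected to settle it sensibly, with any use yes/no under ordinary kappa, or counts under a weighted kappa or an ICC. The size of the problem is conditional: with counts and no weights, the coefficient could be well below the ICC for small errors (0.64 against 0.98 in one assumed setting) or, with few zeros, above it for large ones (0.49 against 0.32). All those figures rest on assumed discordance rates, zero rates and count windows, because the documents give none. The effect on feasibility benchmarks, neuropsychiatric safety and abstinence is nil under any of these readings. No change follows.
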